## Background and Rationale

Of the 37.6M US adults with hearing difficulties, over 1M are profoundly deaf (i.e., unable to hear speech or participate in a normal conversation). An additional 6M to 7M of this US total have hearing loss characterized as severe. Statistics from the National Institute on Deafness and other Communication Disorders (NICD) indicate that a condition called sudden deafness strikes one person per 5,000 every year - usually adults in their 40s and 50s. A 2015 online report by the National Center for Health Statistics indicates that less than 2% of adults who indicated that they had any trouble hearing were deaf. More than 219,000 patients globally have received cochlear implants; over 70,000 patients in the US. The average cost for one cochlear implant can range from \$40,000 to \$100,000 inclusive of all the treatments. Many deaf patients cannot afford a cochlear implant, others (for medical reasons) are not a candidate for an implant.

Fauxsee Innovations, LLC is focused on developing new devices and assistive technology for the underserved blind and deaf communities. The company designed the Roboglasses® product using advanced sensor and haptic technology for providing guidance assistance to the blind. This proposal addresses development of a RoboHear™ product to provide audible speech recognition capabilities for the deaf. RoboHear™ device will use the haptics technology in the Roboglasses® design to communicate speech information to the deaf using touch (haptic) feedback. Roboglasses® design uses a row of Linear Resonant Actuators (LRAs) located in the stems of the glasses frames to communicate distance information to the wearer. RoboHear™ design will use the same haptic devices also located in the stems of a pair of glasses. These glasses can be fitted with clear or prescription lenses as required. RoboHear™ device will convert audio speech into phonemes that are further mapped into distinct haptic effects that are felt by a deaf user in the stems of the glasses.

There is a significant body of research in sound, sound technology, hearing, speech and speech recognition, sound localization, haptics and haptic effects, and research on human ability to utilize alternate technologies and substitute one sense (e.g., touch) for either hearing or seeing in sensing the environment. New technologies such as LRAs significantly offer unique advantages. LRA outputs are not audible or vibratory. They simply touch the user in various programmable ways. The LRAs move in and out to “touch” the user and apply a slight pressure to the skin. These LRAs are commercially available and are present in many commonly used devices such as smart phones and smart watches. The LRAs are innervating mechanoreceptors used in normal cutaneous tactile perception, not vibro-tactile input from the Pacinian receptors, which are sensitive to temporal differences but less sensitive to spatial resolution. Modern speech recognition technology radically changes the speech detection, recognition and coding problem. Modern microelectronics allows sophisticated control using high-performance

[figure not shown]
microprocessor technology. Weisenberger investigated the issues of communication using tactile stimuli  as well as the role of tactile aids in speech perception  and the use of tactile phonemes . Reed and Durlach investigated the subject of information transfer rates and differences in information transfer rates of phonemic codes using both auditory and tactual (haptic) modalities . Tan, et al, have more recently investigated optimum information transfer rates for various modalities . These new technologies now make it much more feasible to build devices that can recognize speech and translate that speech into haptic stimuli.

## Objectives

We are testing the feasibility of using high-performance, low-cost speech recognizers for converting spoken speech into text, translating that text into a phonemic representation and then mapping the phonemes into haptic effects. We will perform a pilot study of 7-9 subjects to develop a training program for teaching users to understand haptic phonetics. We will utilize computer-aided instruction programs to facilitate learning and practice with the device. We hope to show that haptic technology can provide an alternative form of communication for the deaf population.

## Investigational New Device

RoboHear uses high-performance, low-cost speech recognizers for converting spoken speech into text, and translates that text into a phonemic representation. The phonemes are mapped into haptic effects. The haptic devices (LRAs) will be housed in glasses stems that also contain microphones for receiving the audio. This ambitious research effort is feasible because we are able to reuse patented components and subsystems developed for our Roboglasses® product.

### Figure 1

Our initial research indicates that it will only be necessary to fabricate one new hardware item for RoboHear™. This is the Haptic Control function. While our Roboglasses product provides a Haptic Control function, it is implemented on a small (19 x 21 mm) circuit board that is located behind the Roboglasses® lenses. Our RoboHear™ concept calls for all electronics, as well as the haptic devices, to be located in the stems of the RoboHear™ glasses (so that the lenses are unobstructed). It will be necessary to fabricate a flexible printed circuit (FPC) containing the electronics for driving the haptic devices as shown in Figure 1. Note that this is an extremely low-risk effort since the electronics design is the same as that used in Roboglasses® design. It is merely repackaged in a different form factor. This FPC is approximately 131 mm long and 12.3 mm high. The 8mm holes in the FPC surround the LRAs that play the haptic effects. The left end of the FPC is a printed connector for use in interfacing with the Haptics Controller function.

Since Fauxsee has previously developed the software for controlling and activating the proposed LRA devices, we anticipate reusing this software with only minor changes. This software consists primarily of IC software drivers and the code for controlling and activating LRAs. As noted earlier, we will reuse the processor and power manager hardware from our Roboglasses® product and the RoboHear™ design can utilize a large body of existing software for the haptic interface. We plan to use software from the CMU Sphinx project at Carnegie Mellon University. This is a state of the art speech recognition engine that is designed specifically for operation in computer environments with few hardware and software resources .

[figure not shown]
One primary research goal is to investigate and characterize the best mapping between phonemes and haptic effects. We are using LRAs and intelligent haptic drivers for producing haptic effects. Each LRA and haptic driver pair (DRV2605 from Texas Instruments) provides up to 123 different haptic effects. Table 1 describes a few of these haptic sensations. The haptic effects are not audible – they are touch sensations. Note that we are mapping one of 44 phonemes into 1 of 123 different haptic effects. Also note that many haptic effects can be played at different levels of intensity and this may be important in simulating loudness of the speech being processed. This means that the mapping of phoneme to haptic effect must be simple and intuitive thus minimizing cognitive effort for recognition . RoboHear takes advantage of the location of the haptic effects in the row of LRAs on the stems to make it easier to learn. The spatial location allows the differentiation of effects both by the particular haptic sensation and by the location of the effect. Just as a blind person learns to read Braille by distinguishing the location of raised dots, we are using the same concept but simplifying it by taking advantage of the different haptic effects.

**Table 1. Example Haptic Effects**

Effect Description	Effect ID	Effect Description
Strong Click 100%	51	Buzz 20%
Strong Click 60%	52	Pulsing Strong 1 – 100%
Strong Click 30%	53	Pulsing Strong 2 – 60%
Sharp Click 100^%	54	Pulsing Medium 1 – 100%

Figure 2 illustrates our current implementation of RoboHear™ device. This implementation uses the right and left haptics FPCs developed for use with Roboglasses® device. In this implementation, all low-level processing (managing the hardware) is accomplished in a highly integrated Bluetooth LE processor while all high-level processing (speech to text conversion, text to phoneme conversion and phoneme to haptic mapping) is accomplished in an application specific processor. This processor could be the main processor in a cellular telephone (e.g., iPhone) or an application specific processor such as that used in Roboglasses® device. This approach allows all hardware specific processing to be accomplished in the RoboHear™ processor. The embedded electronics in the RoboHear™ glasses frames communicate with the application processor over a Bluetooth LE link. In this implementation, the processor (e.g., a Texas Instruments CC2640) and one microphone are located in the right

glasses stem, and a second microphone and the power manager (controlling battery

charging, voltage regulation, and power consumption) is located in the left glasses stem. The electronics in the stem communicate with each other over a small flat flexible circuit (FFC) routed through the RoboHear™ glasses frames.

Figure 3 shows the power manager and processor cards used in our Roboglasses® product. The 41 x 36 mm processor board (on right in photograph) provides a high-performance 32-bit processor (Texas Instruments TM4C123) that can be used to execute the RoboHear™ software. The figure also shows the Power Manager circuit card used in Roboglasses® device. This 31 x 37 mm card provides a Lithium Ion battery power source and necessary filters and regulators. These two cards provide the necessary power management and processing capabilities required in the RoboHear™ design and can be used without modification to support the proposed Phase I project.

Figure 3. Processor and Power Manager

## Study Design and Procedures

Participants will be asked to learn to recognize haptic sensations (touch) as phonemes and short words or phrases. The haptic sensations are generated by Linear Resonant Actuators (LRAs) situated in the stems (i.e., temple piece) of the RoboHear™ device. The actuators are made of steel but are separated from the participant's skin by a thin elastomeric covering. The covering allows the participant to feel the haptic effect without coming into skin contact with the device. Each glasses stem contains five LRAs. The haptic sensations can be described as a bump, click, purr, buzz, etc. The sensations vary in kind, duration and amplitude. The LRAs do not generate any audible sound. The haptic sensation is not strong enough to cause any pain sensation. The goal is to have

Title: RoboHear™ device: advanced haptic technology that allows the deaf to understand speech  
PI: [name]  
Site: UAMS

the participant learn to associate a particular phoneme with its paired haptic signal, much as user of a smart watch or smart phone can associate a particular function (email, text, call, alarm) with its paired haptic signal.

All trials will take place in a quiet laboratory or office space and will include the participant, a trial manager and optional observers who may include an audiology graduate student or an engineer from Fauxsee who may be present to ensure that software is functioning correctly or to make adjustments in the learning portions of the software (some participants may need a short or longer training session). The participant will be outfitted with the RoboHear™ glasses and will be seated before a computer display. The trial manager will control information presented to the participant with the RoboHear™ haptics. Trials will be conducted in two phases - a learning phase and a recognition phase:

1. In the learning phase, the trial manager will provide the participant with a particular set of haptic stimuli and a display showing the phonetic mapping of the stimuli. Phonetic mapping will be combined with word mapping. This is the same process that is used in teaching children how to read where they are learning to sound out words using phonemes. Here the participant will be learning to feel phoneme while also seeing the word and hearing the word pronounced by the computer program. Participants will be given repeated instruction over the course of a learning period.
2. In the recognition phase of testing, the participant will be presented with various haptic stimuli and will be asked to select or sound the recognize phoneme or word. Data monitoring will be done from a distance from each participant in the trial so that no participant will be affected by the collection of data. Data from our experiments will be recorded by the test coordinator and will include data about the length of time spent on various learning tasks as well as recognition time and recognition accuracy.

## **Study Population**

This pilot study will consist of seven to nine adult participants (18-year old or older). We may consent up to 15 subjects, in order to have 7-9 complete the testing. Participants will need to understand English and must be able to sit at a computer for the training and evaluation session. The session may range from one hour to up to 4 hours in length (with breaks provided as needed). Participants will be recruited from the UAMS TRI Research Participant Registry. If needed, fliers and other advertisements (newspaper, TV, etc.) may be implemented as well.

Inclusion criteria:

Title: RoboHear™ device: advanced haptic technology that allows the deaf to understand speech  
PI: [name]  
Site: UAMS

-18 years and older

-Able to understand and read basic words in English

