## **Data Analysis**

We will analyze the length of time spent on various learning tasks as well as recognition time and recognition accuracy. As this is a small pilot study, most of the statistics will be descriptive. We will use paired t-test to compare recognition accuracy at the beginning and end of training session. We will look to see if any demographic data (age, gender, hearing status, etc.) has any positive or negative effect on learning capability by comparing recognition time and recognition accuracy.

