## **Ethical Considerations**

This study will be conducted in accordance with all applicable government regulations and University of Arkansas for Medical Sciences research policies and procedures. This protocol and any amendments will be submitted and approved by the UAMS Institutional Review Board (IRB) to conduct the study.

The formal consent of each subject, using the IRB-approved consent form, will be obtained before that subject is submitted to any study procedure. All subjects for this study will be provided a consent form describing this study and providing sufficient information in language suitable for subjects to make an informed decision about their participation in this study. The person obtaining consent will thoroughly explain each element of the document and outline the risks and benefits and requirements of the study.

The consent process will take place in a quiet and private room, and subjects may take as much time as needed to make a decision about their participation. Participation

Title: RoboHear™ device: advanced haptic technology that allows the deaf to understand speech  
PI: [name]  
Site: UAMS

privacy will be maintained and questions regarding participation will be answered. No coercion or undue influence will be used in the consent process. This consent form must be signed by the subject or legally authorized representative, and the individual obtaining the consent. A copy of the signed consent will be given to the participant, and the informed consent process will be documented in each subject's research record.

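### Does counting the sample by completers, with no completion proportion planned, call for a change to the plan?

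*Combined protocol and SAP*

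**What the plan says.** Study Population sets the recruitment target: "We may consent up to 15 subjects, in order to have 7-9 complete the testing". The same section describes the study as seven to nine adults, and Risks and Benefits uses the same count for the people exposed to risk. Ethical Considerations adds that consent "will be obtained before that subject is submitted to any study procedure", so a consented person need not have started anything.

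Data Analysis names one test: "We will use paired t-test to compare recognition accuracy at the beginning and end of training session". Otherwise it says "As this is a small pilot study, most of the statistics will be descriptive" and lists learning time, recognition time, recognition accuracy and a look at demographic effects. It does not define an analysis set or say how a missing end score is handled, and it does not list a count of starters and completers.

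Objectives gives the purpose: "We will perform a pilot study of 7-9 subjects to develop a training program for teaching users to understand haptic phonetics". The feasibility named there is that of turning speech into text, then phonemes, then haptic effects. Training takes place in a session of one to four hours with breaks, and Study Design and Procedures allows its length to be adjusted because "some participants may need a short or longer training session".

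**The concern.** If recruitment continues until enough people complete, those who start and give up can drop out of view. A paired test on 9 people looks the same whether 9 of 10 or 9 of 15 starters finished. For a pilot meant to develop a training program, those are different findings.

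There is also a selection worry. If people stop because they cannot learn the code, the accuracy of those who finish overstates how learnable it is for everyone who tries. With up to 15 consents for 7-9 completers, the room for this appears large.

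**Working it through.** **What can be reproduced.** The documents give no significance level, power, effect size, SD or dropout rate behind 7-9 or 15, so there is no stated calculation to reproduce. The room under the cap follows directly:

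- 9 completers: (15 − 9)/15 = 40.0% of those consented do not complete.
- 7 completers: (15 − 7)/15 = 53.3%.

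These are limits if all 15 consents are used and the target is met. They are not expected rates, and they include people who never start.

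**What the missing proportion would show.** Exact (Clopper-Pearson) 95% intervals for two assumed outcomes:

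| Starters | Completers | Proportion | 95% CI |
|---|---|---|---|
| 10 | 9 | 90% | 55.5% to 99.7% |
| 15 | 9 | 60% | 32.3% to 83.7% |

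The intervals overlap widely. At this size the counts and the reasons for stopping carry most of the information.

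**Possible selection effect.** Suppose stopping is governed by a normal variable with correlation ρ to accuracy level, and the lowest-ranked starters stop. The mean of completers then exceeds that of all starters by ρ × (mean of the top k of n standard normal values), in SD units:

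- 10 start, 9 finish: 0.171ρ, so 0 at ρ = 0, 0.05 at ρ = 0.3 and 0.17 at ρ = 1.
- 10 start, 7 finish: 0.457ρ, so 0, 0.14 and 0.46.
- 15 start, 7 finish: 0.809ρ, so 0, 0.24 and 0.81.

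The same expression applies to the mean change only if stopping is related to a person's gain. With true mean gain zero and a two-sided 5% paired t-test (200,000 simulations), 9 finishing of 11 at ρ = 0.3 gives a shift of 0.09 SD and rejection in 5.8% of runs. With 7 of 15 at ρ = 0.5 the figures are 0.41 SD and 17.5%. At ρ = 0 there is no shift and the rate stays at about 5%. The documents supply neither ρ nor the number who stop, so these are conditional illustrations.

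**Would a different counting rule help?** The shift depends on who stops among those who start. A later consent adds another person subject to the same process and does not change which kind of person completes. If 9 start and the weakest 2 stop, the 7 who remain are equally selected whether or not two more are recruited. Counting 7-9 as starters therefore leaves the selection in place and can reduce the pairs. The standardised change detectable by a paired t-test with 80% power (two-sided 5%) is:

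| Pairs | Detectable change (SD of change) |
|---|---|
| 7 | 1.273 |
| 6 | 1.435 |
| 5 | 1.682 |

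**The case for a change.** The strongest case for a change does not need any bias. How many starters get through training is informative for a training program, and the plan does not commit to reporting it. Neither Study Design and Procedures nor Data Analysis lists completion status or reasons for stopping. Nothing says the extra consents are only for people who never start; the target is worded as completing, and a session can run to four hours. Writing down the numbers consented, started and completed, and calling the t-test a completers analysis, would cost a few sentences.

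Much of this stands. The wording does not separate people who never start from people who stop part-way, and the completion share does bear on the training-program aim, though not on the technical feasibility aim. But a result that is not listed in advance is not thereby withheld. Learning time exists for anyone who starts, and the descriptive statistics are not confined to completers. The repeated description of the study as seven to nine participants also fits the reading that the spare consents mainly cover people who never begin, although it does not settle the matter.

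**Conclusion.** No change to the plan follows. Recruiting to a completer target is a fair choice for a pilot this small, because it protects the number of pairs. The alternative of counting starters would remove no selection and could raise the detectable change from 1.273 SD to 1.435 or 1.682 SD if only 6 or 5 pairs remained. The paired test estimates within-person change among people with both scores. Bias in it would need stopping to be related to gain, and no section documents such a link. The selection figures run from zero upward according to assumptions the documents cannot settle, and the largest needs all 15 to start and 8 to leave a session whose training length can be adjusted and which includes breaks.

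What is left is a small gap in written detail: the numbers consented, started and completed, the reasons for stopping, and the plain statement that the t-test rests on people with both scores. This conclusion assumes that the analysts will report that participant flow, as is ordinary for a descriptive pilot, and that they will summarise the data they hold on people who stopped.

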#### Exclusion Criteria

-Less than 18 years old

Unable to understand and read basic words in English

### Risks and Benefits

#### **1. Risk to participants**

The potential risks to seven to nine (7 to 9) adult participants in the proposed studies are minimal. Because working with a desktop computer and wearing a pair of normal weight and size glasses with clear glass are skills and activities that are commonly performed by participants, the participants are not being asked to attempt a novel activity and will not be placed at risk of harm as a consequence of participating in this research.

**Electrical Shock Risk.** Participant will wear a modified version of the RoboHear™ glasses which contain the haptic devices. The glasses stems are connected to a control processor that processes speech into phonemes and then to haptic sensations. All voltages are 3.3 volts or less and there is no danger of electrical shock. No voltage in any part of the system exceeds 5.0 volts (at USB power block).

**Magnetic Field Risks.** Each LRA consists of a spring, moving mass, a voice coil and an extremely small NeFeB Neodymium magnet. There are no other known risks to participants in this study.

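### The protocol names the magnetic field of the ten actuator magnets as a risk, but states no magnet-specific conclusion and no implant question before fitting, so an implant wearer is eligible as written

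*Combined protocol and SAP*

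**What the plan says.** The risk section (Risks and Benefits, 1. Risk to participants) judges the overall risk minimal. The basis it gives is that using a desktop computer and "wearing a pair of normal weight and size glasses with clear glass" are everyday activities. Two specific risks follow.

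- **Electrical shock.** The paragraph gives voltages (3.3 V or less, never above 5.0 V) and concludes that there is no danger.
- **Magnetic field.** The paragraph lists the parts of an actuator, including "an extremely small NeFeB Neodymium magnet". The next sentence is "There are no other known risks to participants in this study".

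On the hardware, Study Design and Procedures states: "Each glasses stem contains five LRAs". The actuators are separated from the participant's "skin by a thin elastomeric covering". The section on the device describes haptic circuits on both the right and the left.

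On who may take part, Study Population requires age 18 or over, basic English and being able to sit at a computer. The exclusion list only mirrors the first two of these; its last entry is "Unable to understand and read basic words in English". On duration: "The session may range from one hour to up to 4 hours in length", with breaks as needed. On numbers: "We may consent up to 15 subjects, in order to have 7-9 complete the testing".

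**The concern.** The sponsor raised magnetic field as a risk and then left the paragraph without a conclusion. The people for whom a magnet near the head could plausibly matter are those with an implanted electronic or magnetic device, and nothing in the visible criteria identifies them.

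Such a volunteer is foreseeable here. The device is meant for deaf people, and Background and Rationale reports over 70,000 cochlear implant recipients in the US. Data Analysis lists hearing status among the characteristics to be compared, so the sponsor expects hearing to vary. In the learning phase participants also hear each word spoken by the computer, and that step does not rule out someone who hears through an implant. Implants other than cochlear ones are not confined to deaf people.

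What is at stake is participant safety at the moment of fitting. No endpoint, test or sample size is affected.

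**Working it through.** The protocol gives no figure of its own to reproduce here. The check is two small sums and a comparison of sections.

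**Number of magnets**

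- Actuators per stem: 5 (Study Design and Procedures).
- Instrumented stems: 2, right and left (Investigational New Device).
- Magnets per actuator: 1 (1. Risk to participants).
- 5 × 2 × 1 = 10 magnets.

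This is a count of parts. It does not measure field or dose.

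**Duration.** The session lasts 1 to 4 hours including breaks. Time with the glasses on is not stated, so 4 hours is a ceiling on the session and not a wearing time.

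**How each section deals with an implant**

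| Section | What it provides | Implants as a safety matter? |
|---|---|---|
| 1. Risk to participants | General minimal-risk judgment; magnet named and called very small | No |
| Study Population; Exclusion Criteria | Age, English, able to sit at a computer | No |
| 2. Adequacy of protection against risks | Anticipated risk assessment, safety briefing, promise to change the procedure if new risks appear | No |
| Data Handling and Recordkeeping | Principal Investigator monitors procedures for safety | No |
| Data Analysis | Hearing status as a comparison variable | No |
| Ethical Considerations | Risks and requirements explained at consent | No |

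A hearing-status item or the consent discussion might bring an implant to light. Even then, no visible text says what staff should do next.

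**Room to exclude**

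- With 9 completers: 15 − 9 = 6 places, 6/15 = 40% of consents.
- With 7 completers: 15 − 7 = 8 places, 8/15 = 53% of consents.

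The same places must cover dropouts. The protocol estimates neither dropouts nor implant wearers, so it cannot be shown that 6 to 8 is enough.

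**The case against.** The strongest reply is that the hazard is not in the documents. They give no field strength and no implant tolerance, and they nowhere say that these actuators can disturb an implant. What they do say is reassuring: the magnets are very small, and Background and Rationale notes that such actuators are common in phones and watches. This stands, and it limits the point to a missing safeguard.

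A reader might nonetheless infer any of four stronger claims. The documents do not support them.

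- **That the glasses endanger implant wearers.** Neither the size of the hazard nor the chance of enrolling a wearer can be derived from the text.
- **That the risk was not considered at all.** The magnetic paragraph sits under a general judgment of minimal risk. That judgment's stated basis, familiarity with glasses and computers, does not address magnets, but it is a conclusion covering the whole section.
- **That staff could not hold off fitting.** The protection section commits the team to change the procedure when a risk is detected, and the Principal Investigator is charged with protecting participants. This is real authority. It is general, however, and gives no rule for an implant.
- **That a wearer would be exposed for four hours.** Only the session length is given, and it includes breaks.

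The consent form was not available and may carry a warning or a question. A warning would inform volunteers but would not change the eligibility criteria. The finding therefore applies to the visible text only.

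**Conclusion.** The point holds in a limited form. Magnetic field is named as a risk of ten magnets at the temples, with no magnet-specific conclusion or precaution. The visible criteria have no implant screen, so a wearer of a cochlear or other implanted electronic or magnetic device is eligible as written.

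The size of the risk is unknown and may be small. The conclusion rests on two assumptions: that the removed consent pages do not already tie an implant question to eligibility, and that a magnet close to the head is worth a question when an implant is present. The second is general caution and is not drawn from the documents.

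Completing the magnetic-field paragraph would on its own be a drafting matter. The screening question is the substantive part, because it changes who is exposed. Severity: consider, as a cheap improvement.

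**What to change.** Add to Study Population and Exclusion Criteria a question, asked before the glasses are fitted, about cochlear or other implanted electronic or magnetic devices. Do not fit a volunteer who has one unless the investigator documents, with IRB agreement, that the field is harmless to that person. While amending, it would be tidy to state the magnetic-field conclusion and its basis in the risk section.

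The cost is one question, one eligibility line and IRB approval of the amendment. Using the exception, or stating a basis in the risk section, would need some supporting information on the field, which the protocol does not contain.

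The downside is that a few volunteers may be excluded without need, and implant wearers may be lost from the hearing-status comparison. The 6 to 8 places beyond the completer target give some room, shared with dropouts, and the documented exception offers a way back in.
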